Motor battery. Pre- and post-op motor assessments are part of routine care for patients with Parkinson's disease. The motor assessments for this study are more extensive and frequent than what occurs as part of routine care. These assessments will be conducted over multiple sessions in the Neuromechanics Laboratory ([name], sub-investigator). In the "practically defined off" medication state (off PD medications for >12 hours), we will measure changes in the cardinal PD symptoms (tremor, rigidity, bradykinesia, dyskinesias) observationally using the UPDRS-part 3 (a standard neurological measure for the diagnosis of movement disorders), along with measures of upper limb dexterity (9-hole pegboard dexterity test, this is a timed test requiring the participant to place 9 separate pegs into holes in a standardize block and then remove them), gait (4-meter walk gait speed, walking backwards, both of these are timed tests require patients to walk given distances), postural stability (limits of stability test, the floor beneath the participant is moved until the patient becomes unstable. Safety is ensured through the use of a safety harness.), compensatory stepping (compensatory stepping test, analyzes stepping patterns and the forces generated by the feet of patients), balance (The activities-specific balance confidence (ABC) scale), and posture (static posture test, a simple observation of the participant's posture) versus pre-op baseline. Further, movements will be measured with 8 camera 3-D motion capture and treadmill force plates, allowing complete parameterization of upper limb dexterity, gait, balance, and other complex movement abnormalities associated with PD. Motor assessments will be obtained prior to surgery and with repeated measures after each portion of the crossover study. This core motor battery will last no more than 1 hour total.

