Cognitive/behavioral, speech, and quality of life batteries: Pre-op neuropsychological testing is part of routine care, however all post-op NP testing is study-related. The medical record will be reviewed for the pre-op testing data. For patient comfort, these evaluations will occur on a different day from the motor battery in the Neuropsychology Laboratory ([name], sub-investigator), with patients on their dopaminergic medications. This battery will measure changes in sensitive, validated measures of verbal fluency, executive function, planning, memory, impulsivity, anxiety, depression, speech intelligibility and acoustics, and patient-centered quality of life assessments versus pre-op baseline. The specific cognitive measures used are the Dementia rating scale-2 (DRS-2), Oral reading recognition, Conners Continuous

Performance Test (CPT-3), Flanker inhibitory control, List sorting working memory, Animals, fruits, and vegetables, Picture vocabulary, AVLT, 10/36 spatial memory, Picture sequence memory, Judgement of line orientation, Trails A and B, Pattern comparison processing, Letter fluency (alt forms), DKEFS Stroop test, Picture vocabulary, Dimensional change card sort, Neuropsychiatric inventory, Beck depression inventory-2 (BDI-2), and the Beck anxiety inventory. Quality of life measures include PD questionnaire 39 (PDQ-39), Freezing questionnaire (FOG-Q), UPDRS-parts 1, 2, and 4, a motor function diary kept by the participant, and an open ended interview. The speech measures include the Rainbow passage, Voice handicap index, Communicative index bank, as well as assessments of spontaneous speech, maximum phonation time, and voicing formants F1 and F2. This comprehensive assessment will last no more than 3 hours per session.

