d. If different phases are involved, what is the duration of each phase in which the participants will be involved? If no phases are involved, enter "not applicable."

Pre-op baseline evaluation: Involves two study visits. One is a motor battery (see 16a above) visit lasting approximately one hour and the other is one cognitive/speech/quality of life evaluation (see 16a above) lasting approximately 3 hours. The pre-op baseline evaluation will take place during month one following enrollment.

DBS implantation surgery: Typical DBS surgeries last between 2-3 hours. Here we will measure cortical activation by DBS with EEG/ECOG/EMG. The actual research portion on the day of surgery will extend the surgical time by no more than 30 minutes. As per routine care, O-arm CT images and post-op MRI images that we will use for DBS lead localization will be gathered as well. DBS electrode implantation surgery will take place during month 2 following enrollment.

Monopolar survey: Here the participant's DBS will be activated and therapeutic settings will be identified. This involves a clinical visit and lasts approximately two hours. In addition, we will assess the participant's movement abilities with our motor battery (see 16a above) lasting approximately one hour. The monopolar survey will take place during month 3 following enrollment.

Crossover study: This portion of the study will involve six separate study visits over the course of 6 months to evaluate three different DBS stimulation conditions. For each condition we will assess our motor battery and field shaping surveys in one visit (see 16a above) lasting approximately one hour and our cognitive/speech/quality of life batteries (see 16a above) in one visit lasting approximately 3 hours. Also, see Table 3 below.

TABLE 3. Summary of research encounters, procedures, and corresponding specific aims.	Pre-op baseline	DBS surgery	Monopolar Survey	Double-blind, randomized crossover to omnidirectional versus directional DBS guided by monopolar survey				Crossover to directional DBS guided by EEG/ECoG	Study exit at 1 year with repeat EEG		
				Condition 1		Condition 2					
Specific Aim(s)	All		1.1 and 1.2		2.1, 2.2, and 2.3						
Encounter number	1a	1b	2	3	4a	4b	5a	5b	6a	6b	7
Encounter duration (hours)	1	3	3-4	3	3	3	3	3	3	3	3
Calendar duration (months)	1		2		3 to 4		5 to 6				12
Medication state	off	on	off	off	on	off	on	off	on	off	off
Motor battery											
Cognitive/behavioral battery											

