Quality of life battery											
Speech battery											
Field shaping survey											
PRISMA MRI with tractography											
ERP assay (EEG/ECoG/EMG)											
O-arm CT for lead localization											
Routine post-op CT brain											

Exploratory Crossover Arm Guided by Electrophysiology Biomarkers: In this nested arm of the crossover study, we will activate a combination of one or more DBS contact segments based purely on electrophysiology from the intraoperative assay. It will involve two study visits over the course of 2 months. For this condition we will assess our motor battery in one visit (see 16a above) lasting approximately one hour and our cognitive/speech/quality of life batteries (see 16a above) in one visit lasting approximately 3 hours.

Study Exit visit: This portion of the study will involve a single visit to serve as a 1 year post-operative follow up to evaluate the long term robustness of our electrophysiological measures. We will reassess portions of our motor battery (see 16a above) and our ERP assay. This visit should last less than 2 hours.

e. List the procedures, the length of time each will take, and the frequency of repetition, and indicate whether each is done solely for research or would already be performed for treatment or diagnostic purposes (routine care) for the population. *Insert additional table rows as needed.*

Please see table 3 above for frequency of repetition. Each measure will be assessed once at each indicated visit.

Procedure	Length of Time Required of Participants (minutes)	Frequency of Repetition	Research (Res) – OR- Routine Care
Measures acquired during DBS surgery			
Intra-op ERP assay	≤30	1 repetition	 Res  Routine
Intra-op O-arm CT	10		 Res  Routine
Post-op brain MRI	30		 Res  Routine
total time (beyond routine care)	≤30		
Motor battery			
UPDRS-part 3	5	7 repetitions (pre-op; monopolar)	 Res  Routine
Therapeutic window	30		 Res  Routine

Activities-specific balance confidence (ABC) scale	3	survey; cross-over visits 4a, 5a, and 6a)	 Res  Routine

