9-hole pegboard dexterity	1		 Res  Routine
4-meter walk gait speed	3		 Res  Routine
Walking backwards	3		 Res  Routine
Compensatory stepping	3		 Res  Routine
Static posture	2		 Res  Routine
Limits of stability	2		 Res  Routine
total time (beyond routine care)	17 per encounter		

Cognitive/behavioral battery

Dementia rating scale-2	20	4 repetitions (pre-op; cross-over visits 4b, 5b, and 6b)	 Res  Routine
Oral reading recognition	3		 Res  Routine
CPT-3	14		 Res  Routine
Flanker inhibitory control	3		 Res  Routine
List sorting working memory	7		 Res  Routine
Animals/fruit/vegetables	5		 Res  Routine
Picture vocabulary	4		 Res  Routine
AVLT (with alt forms)	15		 Res  Routine
10/36 Spatial memory	15		 Res  Routine
Picture sequence memory	7		 Res  Routine
Judgement of line orientation	5		 Res  Routine
Trails A and B	10		 Res  Routine
Pattern comparison processing	3		 Res  Routine
Letter fluency (alt forms)	3		 Res  Routine
DKEFS Stroop test	10		 Res  Routine
Picture vocabulary	7		 Res  Routine
Dimensional change card sort	4		 Res  Routine

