ii. Describe any other alternative treatments or interventions:

DBS is an elective procedure done as part of routine care. Alternative treatments include not participating in the study and being implanted with the device that is currently commercially available instead or to not have a DBS device implanted at all. Patients choosing the latter would continue only with drug therapy for control of their Parkinson's symptoms.

iii. Describe any withholding of, delay in, or washout period for standard of care or alternative treatment that participants may be currently using:

We will ask our participants to delay taking their Parkinson's medications prior to each clinical visit. We are interested in testing the effects of the brain stimulator alone and in order to adequately assess this, our participants need to be in the clinically defined "off" medication state.

d. Do you foresee that participants might need additional medical or psychological resources as a result of the research procedures/interventions? Yes No
If Yes, describe the provisions that have been made to make these resources available.

e. Do the benefits or knowledge to be gained outweigh the risks to participants? Yes No
If No, provide justification for performing the research: _____

19. Precautions/Minimization of Risks

a. Describe precautions that will be taken to avoid risks and the means for monitoring to detect risks.

1. Loss of privacy: Information obtained about patients will be kept private to the extent allowed by law. Identifying information may be shared with the UAB Institutional Review Board (IRB) and others who are responsible for ensuring compliance with laws and regulations related to research. Each participant will be assigned a randomly generated identification number. All information and data will be grouped by identification number which is linked to participant name in a linking document. This linking document will be kept in a locked safe behind a locked door in the PI's laboratory space in the Sparks Center. In publications or presentations

of the data, subjects will not be identified by name. All digital data including camera images of participant's movements will be stored in password protected computers in the PI's laboratory behind a locked door. Hard copies of data will be kept in the same safe described above.

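### Table 3 and section 16.a of the protocol give opposite medication states for all six crossover visits, and the SAP does not say which applies to any endpoint

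*Protocol*

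**What the plan says.** Four places in the protocol bear on this.

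- **Section 16.a, Motor battery.** UPDRS part 3 and the other motor tests are done off medication: "In the 'practically defined off' medication state (off PD medications for >12 hours". On timing: "Motor assessments will be obtained prior to surgery and with repeated measures after each portion of the crossover study". Changes are measured against the pre-op baseline.
- **Section 16.a, Cognitive/behavioral, speech, and quality of life batteries.** These are done on another day, in another laboratory, "with patients on their dopaminergic medications".
- **Section 16.d, Table 3, with the lists in 16.e.** The table gives "Encounter number 1a 1b 2 3 4a 4b 5a 5b 6a 6b 7" and, beneath it, "Medication state off on off off on off on off on off off". Section 16.e assigns the motor battery to "cross-over visits 4a, 5a, and 6a" and the three non-motor batteries to "cross-over visits 4b, 5b, and 6b".
- **Section 18.c.iii.** "We will ask our participants to delay taking their Parkinson's medications prior to each clinical visit". The reason given is that the stimulator's effect is to be tested by itself.

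The SAP lists change in UPDRS part 3 and in PDQ-39 among the data for the primary SA2.3 analysis. It gives a medication state for neither, nor for any other endpoint.

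**The concern.** Two parts of the same protocol tell staff opposite things about the condition under which a primary SA2.3 variable is measured. The SAP cannot settle it. The pre-op visits do not share the conflict: the motor visit is off and the non-motor visit on in both places. Anyone following Table 3 would therefore change the medication state between baseline and crossover.

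Three results would be affected.

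- **UPDRS part 3 change from baseline** would contain a drug effect as well as a stimulation effect.
- **Field-shaping therapeutic windows** are measured at the crossover motor visits. Section 16.a defines the floor of the window by improvement in arm rigidity, a motor sign that medication can itself alter. Table 3 has encounter 3, the monopolar survey, off medication, so windows from the two surveys might not be comparable.
- **The cognitive safety criterion (Milestone 2.7)** counts declines in test scores. Off-medication scores against an on-medication baseline would confound stimulation with drug withdrawal.

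**Working it through.** **1. Align the table.** The encounter, duration and medication rows of Table 3 each have 11 entries. Section 16.d describes the pre-op visits as a one-hour motor visit and a three-hour non-motor visit, which matches the durations of 1a and 1b.

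| Encounter | Battery (16.d, 16.e) | State in 16.a | State in Table 3 | Agree |
|---|---|---|---|---|
| 1a | motor | off | off | yes |
| 1b | non-motor | on | on | yes |
| 4a, 5a, 6a | motor | off | on | no |
| 4b, 5b, 6b | non-motor | on | off | no |

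Six of six crossover visits conflict; both baseline visits agree.

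**2. Could this be an extraction shift?** The sequence implied by 16.a, taking encounters 2, 3 and 7 as off, also has seven off and four on entries. It differs from the row as supplied only in that one off entry sits before 4a instead of at the end. The count of entries therefore cannot exclude a shift. Against a shift, the visibly displaced rows of the table (column headings, aims, calendar months) are merged cells padded with blanks, whereas the medication row has no blanks.

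**3. Change from baseline.** Inclusion criterion 12 requires at least 30% motor improvement on medication. Taking 30% as the drug effect, with no stimulation effect, the apparent change is 0.30 × baseline. The baselines are assumptions:

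- baseline 30: 9 points
- baseline 40: 12 points
- baseline 50: 15 points

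**4. Contrast between strategies.** For strategies A and B with a shared baseline, (A − baseline) − (B − baseline) = A − B, so the baseline's state drops out. As an illustration, assume a baseline of 40, stimulation multiplying the score by 0.80 under A and 0.75 under B, and medication multiplying it by 0.70:

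- Both off: A = 32, B = 30, contrast 2.0; changes from baseline −8 and −10.
- Both on: A = 40 × 0.70 × 0.80 = 22.4, B = 40 × 0.70 × 0.75 = 21.0, contrast 1.4; changes from baseline −17.6 and −19.0.
- A on, B off: contrast 22.4 − 30 = −7.6.

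The changes from baseline are badly distorted. The contrast keeps its sign and shrinks to 1.4/2.0 = 70% when both visits share a state. It goes seriously wrong only when the state differs between visits of one patient.

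**5. What attenuation could cost.** If a fraction r of the contrast is lost and the SD of the paired differences is unchanged, the required sample grows by 1/(1 − r)². That is 1/0.7² = 2.04 at r = 0.3 and 1/0.4² = 6.25 at r = 0.6. For an assumed standardized paired effect of 0.53 (80% power with n = 30, two-sided 0.05), power falls to 50% and 20% respectively. If the SD shrinks in the same proportion, nothing is lost. The documents give neither r nor the SD.

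**The case against.** The strongest objection is that the conflict may lie in the copy and not in the plan. Moving one entry reconciles the row with the prose, other rows of Table 3 are plainly displaced, and its battery marks are lost. This stands as a reason for moderate confidence and for checking the original table first. It does not dispose of the point, for the reason in step 2 of the working.

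The prose also largely supports off-medication motor testing. Section 19.a item 6 ties the off-medication assessments to the motor laboratory, and 16.a gives staff an explicit withholding period. That makes the prose the more likely intention, but it does not correct the table.

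Section 18.c.iii is weaker evidence. Its stated reason concerns stimulation testing, and 16.a calls the post-op neuropsychological testing study-related, so the clinical visits it mentions may not include those sessions. Read literally, it still sits badly with on-medication non-motor testing.

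A reader might infer that the comparison of programming strategies is masked, or that the effective sample is halved. The documents do not support either. The shared baseline cancels, and the factor of 2.04 needs both proportional attenuation and unchanged noise. The 30% response is a pre-implantation eligibility figure. It is no guaranteed floor with stimulation on, and section 18.c.i says DBS often lowers drug needs. Patient preference, also in the primary analysis, is not a score taken at a motor visit, and Table 3 has SA1.1 contact testing at encounter 3 off medication.

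**Conclusion.** The contradiction holds on the text supplied, with moderate confidence pending sight of the original Table 3. It covers six of six crossover visits, and the SAP does not resolve it.

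If Table 3 were followed, UPDRS part 3 change from baseline would combine drug and stimulation effects. The 9 to 15 points are illustrative and rest on assumed baselines and on the eligibility response carrying over. Therapeutic windows from the field shaping survey would be affected where they are compared with windows measured off medication; a comparison within one session shares its state. The Milestone 2.7 comparison with baseline would be confounded. A reader might expect that to exaggerate decline, but the documents give no drug effect on these tests, so the direction is not established.

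The SA2.3 contrast between strategies would not be biased if all three motor visits share one state. It might be attenuated, by an unknown amount that could be nil. It would gain noise only if staff applied different states at different visits. This is a single-centre study, so the risk of inconsistency lies between staff or visits and not between sites.

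**What to change.** First check the medication row against the original Table 3. Then reconcile Table 3, section 16.a, the visit lists in 16.e and section 18.c.iii so that each battery has one stated medication state, the same at pre-op baseline and at every crossover visit. If the original table already matches 16.a, what remains is to clarify 18.c.iii and to complete the SAP. The choice of state belongs to the investigators.

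In the SAP, state the medication state for each endpoint, including UPDRS part 3, PDQ-39, therapeutic window and the cognitive measures. Record the actual state, or the time since the last dopaminergic dose, at each visit. Flag any score taken in a different state from that patient's baseline. For any visits already completed, recover the state from source records.

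The cost is a correction to the protocol wording and table, a short SAP addition and one field on the visit form. No visit or procedure is added.

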Neuropsychiatric inventory	15		 Res  Routine
Beck depression inventory-2	7		 Res  Routine

Beck anxiety inventory	7		 Res  Routine
total time (beyond routine care)	164 per encounter		
Quality of life battery			
PD questionnaire 39 (PDQ-39)	15	4 repetitions (pre-op; cross-over visits 4b, 5b, and 6b)	 Res  Routine
Freezing questionnaire (FOG-Q)	7		 Res  Routine
UPDRS-parts 1, 2, and 4	30		 Res  Routine
Motor function diary	15		 Res  Routine
Open ended interview	30		 Res  Routine
total time (beyond routine care)	67 per encounter		
Speech battery			
Rainbow passage	3	4 repetitions (pre-op; cross-over visits 4b, 5b, and 6b)	 Res  Rout
Spontaneous speech	5		 Res  Rout
Maximum phonation time	3		 Res  Rout
Sustained phonation of vowels	3		 Res  Rout
Formants (F1 and F2)	5		 Res  Rout
Voice handicap index	10		 Res  Rout
Communicative index bank	2		 Res  Rout
total time (beyond routine care)	31 per encounter		
Study Exit visit			
ERP assay	≤30	1 repetition	 Res  Routine
UPDRS-part 3	5		 Res  Routine
Therapeutic window	30		 Res  Routine
9-hole pegboard dexterity	1		 Res  Routine
4-meter walk gait speed	3		 Res  Routine
total time (beyond routine care)	≤34		

f. Will an interview script or questionnaire be used? Yes No
If Yes, attach a copy.

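### At crossover visits 4b, 5b and 6b the non-motor session is limited to 3 hours, but the protocol's own item times add to about 4.0–4.9 hours, and no test order or truncation rule is given.

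*Protocol*

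**What the plan says.** - Protocol 16.a (cognitive/behavioral, speech and quality of life batteries) describes the three batteries together and limits them: "This comprehensive assessment will last no more than 3 hours per session".
- Protocol 16.d, crossover study, places "our cognitive/speech/quality of life batteries (see 16a above) in one visit lasting approximately 3 hours" for each condition. The pre-op entry in 16.d is similar: "the other is one cognitive/speech/quality of life evaluation (see 16a above) lasting approximately 3 hours". Table 3 also shows 3 hours for these encounters.
- The 16.e table gives minutes for each item and a total for each battery: cognitive/behavioral "164 per encounter", quality of life "67 per encounter", speech "31 per encounter". All three are assigned to the same four occasions: pre-op, 4b, 5b and 6b. The text above the table says that each measure is done once at each of its visits.
- The SAP (SA2.3) lists PDQ-39 with patient preference and UPDRS part 3 as the data for the primary mixed-model analysis. Cognitive, behavioral and speech measures are secondary.
- Neither document gives an order of testing or says what is left out if time runs short, and the SAP has no rule for missing data.

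**The concern.** The three printed battery totals exceed 3 hours by a wide margin when added, and one of them does not match its own items. Staff who follow the protocol at a crossover visit must either run past the stated limit or leave something out, and nothing tells them which.

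The comparison of programming strategies is within participant. If what is left out differs between visits or between patients, missing values enter the treatment contrasts directly. The measures exposed are PDQ-39 in the primary analysis and the secondary cognitive and speech outcomes. The 3-hour figure also understates the visit length in the document that the IRB reviews.

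**Working it through.** **Inputs.** All minutes come from the 16.e table. The limit of 3 × 60 = 180 minutes comes from 16.a.

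**Step 1: reproduce the printed battery totals.**

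- Cognitive/behavioral, 20 rows: 20+3+14+3+7+5+4+15+15+7+5+10+3+3+10+7+4+15+7+7 = 164. Printed 164; agrees.
- Speech, 7 rows: 3+5+3+3+5+10+2 = 31. Printed 31; agrees.
- Quality of life, 5 rows: PDQ-39 15 + FOG-Q 7 + UPDRS parts 1, 2 and 4 30 + diary 15 + interview 30 = 97. Printed 67; **does not agree**.

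The gap is 97 − 67 = 30 minutes. Two rows take 30 minutes (UPDRS parts 1, 2 and 4, and the open-ended interview), and leaving out either gives 67. The table's convention of counting only time beyond routine care does not explain the gap, because all five rows are marked as research. The motor battery applies that convention correctly: its total of 17 leaves out the two rows marked routine.

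**Step 2: add the session and compare it with 180 minutes.**

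| Reading of the session | Minutes | Hours | Over the limit |
|---|---|---|---|
| All items: 164 + 97 + 31 | 292 | 4.87 | 112 (62%) |
| Printed subtotals: 164 + 67 + 31 | 262 | 4.37 | 82 (46%) |
| All items less diary (15) and interview (30) | 247 | 4.12 | 67 (37%) |
| Also less the 7-minute Picture vocabulary row | 240 | 4.00 | 60 (33%) |
| Also less UPDRS parts 1, 2 and 4 (30) | 210 | 3.50 | 30 (17%) |
| Cognitive + speech only: 164 + 31 | 195 | 3.25 | 15 (8%) |

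The exclusions in the third and fourth rows have some basis in the text. Item 16.a describes the diary as kept by the participant. The crossover section of 16.a describes an open-ended exit interview at the end of the study. Picture vocabulary is listed twice, at 4 and at 7 minutes. Nothing suggests that UPDRS parts 1, 2 and 4 fall outside the session; that row of the table only tests how far the list would have to shrink. No reading includes breaks or changeover time.

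**Step 3: PDQ-39 on its own.** It takes 15 minutes, and the whole quality-of-life battery takes 67 to 97. Either fits easily in 180. If the cognitive battery is run first, 180 − 164 = 16 minutes remain, just enough for PDQ-39 and nothing else. Whether PDQ-39 is completed therefore depends on the order of testing.

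**Step 4: the pre-op visit.** Item 16.a calls pre-op neuropsychological testing routine care and takes its data from the medical record. If it is done separately, what remains is 97 + 31 = 128 minutes (98 with the printed subtotal), which fits. Items 16.d and 16.e nevertheless list cognitive testing at pre-op, so that visit is ambiguous.

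**The case against.** The strongest reply is that this is a bookkeeping conflict with no shown effect on the primary analysis. The item times may be generous planning figures. The diary and some questionnaires may be completed elsewhere. The interview may be held only once. PDQ-39 is short, and it is one of three primary data items, so a careful team would obtain it.

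Much of this is fair and limits what can be claimed:

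- A reader might infer that PDQ-39, or the quality-of-life battery, cannot be completed. The documents do not support that; only the combined session fails to fit.
- A reader might infer that the limit is broken at all four occasions. It is firm for 4b, 5b and 6b only, given the routine-care statement about pre-op testing.
- A reader might assume that the interview is the item missing from the 67. UPDRS parts 1, 2 and 4 would give the same figure.
- A reader might infer that participants are told the wrong duration. The consent pages were not available, so this cannot be judged.
- Fatigue, or loss of the on-medication state over a longer session, is plausible, but the documents give no data on either. The conclusion does not rest on it.

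The reply does not remove the conflict. The session exceeds 180 minutes with the diary, the interview and the repeated row taken out, and exceeds it before any quality-of-life item is counted. Splitting the batteries over several sessions is not the written plan, because 16.d puts them in one visit. If the item times are too generous, the table needs correcting instead, and the protocol does not say so.

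**Conclusion.** The point holds for crossover visits 4b, 5b and 6b. The listed session takes 292 minutes by item times and 262 by the printed subtotals. It takes about 240 under the most lenient reading with support in the text. Against 180 minutes the overrun is 60 to 112 minutes, or 33% to 62%. The quality-of-life subtotal is a separate error: 67 printed, 97 by its items.

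This rests on two assumptions: that the tabulated minutes are the intended times, and that the three batteries share one visit as 16.d states.

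The consequence for the data is a risk of inconsistent truncation, because no order or stopping rule is given. It touches PDQ-39 as one of three primary data items and the secondary cognitive and speech outcomes. Harm to the primary analysis is possible but not shown. The correction should still be made, since the session cannot be carried out as written and the remedy is cheap.

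**What to change.** 1. In 16.e, correct the quality-of-life subtotal to 97 for the five items listed.
2. State whether the diary and the interview belong in the session, and at which visits. Remove or explain the second Picture vocabulary row, and recompute the totals accordingly.
3. Then either restate the session length in 16.a, 16.d and Table 3 to match the result (about 4.0–4.9 hours), or shorten the list to fit 3 hours. Shortening means removing 60 to 112 minutes, depending on step 2.
4. State whether cognitive testing at pre-op is a study procedure or is taken from the record.
5. Use one fixed test order at every visit with PDQ-39 first. If a session stops early, the same late items are then lost under each condition, and PDQ-39 is not among them.
6. If the consent form repeats the 3-hour figure, carry the corrected length into it.

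The cost is wording and a running order, plus either a longer stated burden for participants or a shorter secondary battery.
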